## **Eating Attitudes**

The Dutch Eating Behavior Questionnaire (DEBQ; 13) is a 46-item questionnaire with three subscales measuring restrained, external, and emotional eating. Responses are recorded on a 5-point Likert scale. These three scales demonstrated strong internal consistency (Cronbach's alpha = 0.80 - 0.95), interrelationships between scales, and factorial validity.

#### Food Craving

The Food Craving Inventory (FCI) will assess the degree of craving for high- and low-fat/sugar foods (14). This scale has shown internal consistency ( $\alpha$ = .93), 2-week test-retest reliability (r = .86), and sensitivity to detecting change.

# Self-report Impulsivity

The Barratt Impulsivity Scale (BIS-15) is a 15-item self-report assessment that will measure attentional, motor, and non-planning impulsivity (15). This scale has shown internal consistency ( $\alpha$ =.81), 2-week test-retest reliability (r=.88), and discriminates between psychiatric patients and controls (56).

#### Acute and Habitual Dietary Intake

Participants will complete our adapted version of the Block Food Frequency Questionnaire (Block FFQ) which inquiries about the frequency of consumption of 60 specific foods over the

past 2 weeks (16) to measure habitual dietary intake. Food frequency questionnaires are the most practical and economical method for collecting dietary intake data in large studies (17). Block FFQ values correlated (r = .57) with 4-day food record estimates for energy and most nutrients (18). We have successfully used this version in previous studies (NORC5-34387, HHSN275201300015C) and published results.

#### Additional Surveys

We will administer the Short-Form International Physical Activity Questionnaire (IPAQ), which queries about physical activity over the previous days and has shown strong reliability (r = .80; (19)). Participants will also complete a modified version of the Pittsburgh Sleep Quality Index, which will ask about sleep quality over the past week (20), which we can determine the previous night's sleep. Lastly, participants will complete the Edinburgh Handedness Inventory, which is a continuous measure of hand dominance (21).

All Surveys will be administered via an iPad using Qualtrics software and applications.

## H. Study Intervention

- Bromocriptine-QR cycloset; 1.6mg; once; oral
- Placebo; 2 capsules; once; oral

Participants will be administered two placebo pills at one testing visit and a two 0.8mg dose of bromocriptine at the other visit. Bromocriptine dose agrees with optimal dose according to clinical trials (22,10). Adverse effects related to bromocriptine include nausea, dizziness, fatigue, headache, diarrhea, and constipation (11). However, adverse events (AEs) are generally not severe; according to Scranton & Cincotta, 17% subjects on bromocriptine reported adverse drugs experiences as severe, while 14% on placebo reported AEs as severe (22). Moreover, the most commonly reported adverse event, nausea, was not reported as severe (22). To prevent any potential adverse interactions with bromocriptine, participants will be asked to abstain from any drugs for 12 hours before the assessment including over the counter pharmaceuticals such as (ex. Advil, aspirin, Benadryl), and for the remainder of the day after the session. Participants will be asked to avoid consuming alcohol for 24 hours after bromocriptine administration to prevent increased risk of drowsiness. Bromocriptine may decrease the effectiveness of oral contraceptives, female participants taking oral contraceptives will be asked to refrain from intercourse for 24 hours or to use an additional form of birth control. Because the half-life for bromocriptine is 6 hours after 24 hours the amount of active drug in the participant's system will have decreased 98%.

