# 2. Testing Visits - Outline

At the Neuropsychology of Ingestive Behavior Lab

Baseline: Fasting blood draw, fasting drug or placebo administration

Baseline-60 minutes: Visual analogues scales (VAS) hunger and satiety, height and weight measurement, demographic and psychological surveys, waiting for drug to become active 60 minutes: Walk to Biomedical Research Imaging Center

At the Biomedical Research Imaging Center

90 minutes - 150 minutes: VAS hunger and satiety, MRI assessment, taste administration, resting state, anatomical scans

At the Neuropsychology of Ingestive Behavior Lab

150 minutes-180 minutes: VAS hunger and satiety, fixed milkshake consumption

180 minutes: Blood draw

180 minutes-210 minutes: Behavioral impulsivity, surveys

210 minutes: Blood draw

210-240 minutes: VAS ratings, hedonic ratings, ad libitum food intake

The testing visit will last approximately 4 hours. Testing visit occurs twice for each participant.

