# Visual Analogue Scale

Visual Analogue Scales will be used to assess hunger, fullness, thirst, and nausea periodically throughout the testing visits. These will be distributed via iPad on Qualtrics software.

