## J. Safety Management

It is possible that the questionnaires may cause distress or embarrassment to the participants. One potential risk to participants is that it may be distressing to disclose information about

psychiatric difficulties. In our estimation, there is a low risk of this possibility and the effects would probably be short-lived. We have conducted several thousand of these types of interviews with no adverse events. We will take steps to minimize this risk by informing them that their data will be confidential. Additionally, it is possible someone maybe embarrassed to be weighed. The research staff will be trained to be highly professional for the entire study visit. Data will be obtained from participants through surveys, taste assessments, height and weight measurements, fMRI scans, blood draws, and saliva. There is a slight risk that these research records might be obtained by persons not authorized to do so. There is also a risk that participants may not understand the limits of confidentiality (i.e. that we will not keep certain information confidential, such as spontaneous disclosures on their part regarding suicidal ideation and child abuse [no measures inquire about sensitive topics such as these]). Data for all participants will be kept strictly confidential, except as mandated by law. All research files will be kept in locked file cabinets in a locked room in a locked building. Participants will be assigned a numerical code for identification in the files. Names and other identifiers will be kept in separate locked files and will never be recorded on any data forms. Statistical analyses will be performed on aggregate-level data; participants are never individually named. All entered data will be kept on the password protected, secured computers or networks at the research site. These data will be accessible only to research staff, using confidential usernames and passwords. All staff on this project will receive training in the ethical conduct of research with human participants prior to contact with data or research participants. Participants will be informed in detail about the limits of confidentiality, including disclosure of intentions to inflict harm to self or others and the possibility that we might break confidentiality to report suspected child or elder abuse. All participants will be told that participation is voluntary and that they may terminate their involvement at any time without any consequences. If, during any assessment, the project coordinator determines that a participant has developed a serious health problem, efforts will be made to help the participant access appropriate treatment as quickly as possible. In addition, any scans that suggest possible problems are sent to a radiologist for a consult. In the event of a potential problem, [name] will meet with the participant and the radiologist to discuss the findings, per protocol from the Biomedical Research Imaging Center.

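### Five of the six bromocriptine side effects that the protocol names are never asked about, and no symptom collection is described after the four-hour visit

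*Protocol*

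**What the plan says.** - **Known effects.** Protocol Section H: "Adverse effects related to bromocriptine include nausea, dizziness, fatigue, headache, diarrhea, and constipation (11".
- **Precautions lasting a day.** The same section says "Participants will be asked to avoid consuming alcohol for 24 hours after bromocriptine administration to prevent increased risk of drowsiness", and that "female participants taking oral contraceptives will be asked to refrain from intercourse for 24 hours or to use an additional form of birth control". It then states: "Because the half-life for bromocriptine is 6 hours after 24 hours the amount of active drug in the participant's system will have decreased 98" per cent.
- **Symptoms recorded.** Protocol Section G, Visual Analogue Scale: "Visual Analogue Scales will be used to assess hunger, fullness, thirst, and nausea periodically throughout the testing visits".
- **Length of observation.** Protocol Section F.2: "The testing visit will last approximately 4 hours". Dosing is at baseline, and the last listed activity is "210-240 minutes: VAS ratings, hedonic ratings, ad libitum food intake". Section C puts two weeks between the testing visits.
- **Safety management.** Protocol Section J deals with questionnaire distress, embarrassment at being weighed, confidentiality and incidental scan findings. Its general health provision begins "If, during any assessment, the project coordinator determines that a participant has developed a serious health problem". The study drug does not appear in the section.
- **Analysis.** In SAP Section B, nausea appears only as a control variable: in the behavioral models for assessments made after the scan, and in the stop-signal models. The SAP has no adverse-event or tolerability summary.
- **Expected losses.** Protocol Section D and SAP Section A both count side effects of the drug among the reasons for enrolling 50 to obtain 42 with usable data.

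**The concern.** This is a blinded, placebo-controlled crossover in which every participant takes the drug once and placebo once. If the same symptom questions were asked at both visits, each participant would serve as his or her own control for tolerability. As written, the plan asks about one of the six effects that it expects the drug may cause, and uses the answer only to adjust other models.

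Two things are at stake. The first is safety ascertainment. Participants walk to the imaging center from minute 60, about when Section C says the drug becomes active, yet dizziness is not asked about. The effects least likely to show within a few hours, diarrhea and constipation, have no point of collection at all. The second is reporting. The plan expects side effects to cost usable data but gives no means of describing them by treatment. Fatigue or drowsiness data would also help in reading the reaction-time results, though that benefit is secondary.

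**Working it through.** **1. The plan's own figure: drug decrease at 24 hours.** Inputs from Section H: half-life 6 h, elapsed time 24 h, stated decrease 98%. With first-order elimination, decrease = 1 − 0.5^(t / half-life).

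- 24 / 6 = 4 half-lives, so 1 − 0.5^4 = 1 − 0.0625 = 93.75%. The stated 98% is not reproduced.
- A 98% decrease needs ln(0.02) / ln(0.5) = 5.64 half-lives. That is 5.64 × 6 = 33.9 h at a 6-hour half-life, or a half-life of 24 / 5.64 = 4.25 h if 24 hours is kept.
- Other starting points do not rescue it. From a peak at 90 minutes (22.5 h elapsed) the decrease is 92.6%. Taking the 24 hours from the end of the visit (28 h after dosing) gives 96.1%.

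The documents do not show which of the three figures is wrong.

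**2. Named effects against what is collected.**

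| Effect named in Section H | Asked during the visit | Asked after the visit | Use in the SAP |
|---|---|---|---|
| Nausea | Yes (VAS) | No | Control variable only |
| Dizziness | No | No | None |
| Fatigue | No | No | None |
| Headache | No | No | None |
| Diarrhea | No | No | None |
| Constipation | No | No | None |

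Not solicited: 5 of 6. The other instruments in Section G cover eating attitudes, craving, impulsivity, diet, physical activity, sleep and handedness. The sleep questionnaire looks back one week, so after a two-week interval it would not reach the night following the first testing visit. In the F.2 outline the first listed VAS falls in the interval that starts at dosing, so no pre-dose symptom reading is shown either.

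**3. Timing.**

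- Dosing at 0; drug active at about 60 min (Section C); scanning timed to maximum concentration at about 90 min (Section G); visit ends at about 240 min.
- The Section H precautions run to 24 h, and 24 − 4 = 20 h of that period have no described symptom collection.
- On the stated half-life, 0.5^(4/6) = 63% of the drug remains at the end of the visit if the whole dose is counted from time zero. Counted from a peak at 90 min, the level is 0.5^(2.5/6) = 75% of peak. Both describe drug still present, not a share of reactions.

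**4. Where an event would go.** Section J provides for serious problems identified during an assessment. It gives no adverse-event definition, recording form, causality step or reporting route. The SAP tabulates no events. Yet SAP Section A lists medication side effects among the reasons for the margin of 50 − 42 = 8 participants.

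**The case against.** **Reactions may still be seen.** A reader might infer that most drug reactions would go unseen. The documents do not support that: they give no onset times and no single-dose reaction rates. Onset of activity and peak level both fall inside the visit, when staff may notice a reaction or a participant may volunteer it. A symptom that is not solicited is not necessarily missed. This part of the objection stands.

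**Events can be attributed.** A reader might also infer that reactions could not be linked to treatment. One blinded treatment is given per visit, the visits are two weeks apart, and a randomization key is held. Any dated event can be assigned to drug or placebo. This stands too.

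**Contact after discharge may exist.** It is tempting to say that a late reaction would reach nobody. Consent and contact pages are absent from the text available for review and may carry such instructions, so that conclusion cannot be drawn.

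**The 24 hours is not a symptom window.** Section H sets it for alcohol and oral contraceptives, which are interaction precautions. It is therefore wrong to treat 4 of 24 hours as the fraction of reactions observed.

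**Cited severity rates do not give a size.** Applying the 17% and 14% in Section H to 50 participants gives 8.5 and 7. Those rates count severe events only, and the protocol does not show that they carry over to a single dose. They should not be used as a projection.

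**No aim concerns tolerability.** That is so. In addition, reaction time is exploratory, the SAP specifies no resting-state analysis, and unmeasured drowsiness does not bias the placebo-controlled contrast. This limits the weight of the point. It does not remove the gap between the effects that Section H names and what is collected.

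**Conclusion.** The point holds as a gap in systematic collection and reporting. Five of the six named effects have no planned question, the sixth serves only as a covariate, and none is collected after the visit. The drug is missing from the safety section, and the SAP has no safety summary. How many reactions this would miss cannot be estimated from the documents.

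This is an inexpensive improvement, not a threat to the primary comparisons. It assumes that no adverse-event form or follow-up contact is set out in material outside the available text.

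The inconsistency between a 6-hour half-life and a 98% decrease at 24 hours is a separate, arithmetical finding. It needs only first-order elimination and the protocol's own numbers.

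**What to change.** 1. **During the visit.** Add items for dizziness, fatigue or drowsiness, and headache to the existing Qualtrics VAS, identically at both testing visits, with one set before dosing and one before the visit ends.
2. **After the visit.** Collect a short symptom questionnaire on all six named effects for the day after dosing, by automated Qualtrics message after each testing visit, with a look-back at the start of the second. Identical timing at both visits preserves the blind and makes the two periods comparable.
3. **Documents.** List the study drug as a risk in Section J. Add to the SAP a descriptive table of solicited symptoms and adverse events by treatment period. How responses are reviewed and managed is for the sponsor to decide.
4. **Section H.** Reconcile the half-life, the 98% and the 24-hour window.

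Cost: a few survey items, one message per visit on software already in use, and one table. The VAS sets become slightly longer, and some participants will not answer the follow-up questionnaire, so the response rate should be shown beside the table.

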#### I. Study Intervention Administration

This is a within subjects designed experiment, so all subjects will receive the Cycloset and placebo. The administration will be blinded to subject and the research. [name] will oversee the blinding procedure. The order of the drug and placebo will be counterbalanced across the two visits, and [name] will see to the drug/placebo administration schedule. Because the screening visit is before the testing visit and randomization we are confident in the participant's eligibility.

## J. Safety Management

It is possible that the questionnaires may cause distress or embarrassment to the participants. One potential risk to participants is that it may be distressing to disclose information about

psychiatric difficulties. In our estimation, there is a low risk of this possibility and the effects would probably be short-lived. We have conducted several thousand of these types of interviews with no adverse events. We will take steps to minimize this risk by informing them that their data will be confidential. Additionally, it is possible someone maybe embarrassed to be weighed. The research staff will be trained to be highly professional for the entire study visit. Data will be obtained from participants through surveys, taste assessments, height and weight measurements, fMRI scans, blood draws, and saliva. There is a slight risk that these research records might be obtained by persons not authorized to do so. There is also a risk that participants may not understand the limits of confidentiality (i.e. that we will not keep certain information confidential, such as spontaneous disclosures on their part regarding suicidal ideation and child abuse [no measures inquire about sensitive topics such as these]). Data for all participants will be kept strictly confidential, except as mandated by law. All research files will be kept in locked file cabinets in a locked room in a locked building. Participants will be assigned a numerical code for identification in the files. Names and other identifiers will be kept in separate locked files and will never be recorded on any data forms. Statistical analyses will be performed on aggregate-level data; participants are never individually named. All entered data will be kept on the password protected, secured computers or networks at the research site. These data will be accessible only to research staff, using confidential usernames and passwords. All staff on this project will receive training in the ethical conduct of research with human participants prior to contact with data or research participants. Participants will be informed in detail about the limits of confidentiality, including disclosure of intentions to inflict harm to self or others and the possibility that we might break confidentiality to report suspected child or elder abuse. All participants will be told that participation is voluntary and that they may terminate their involvement at any time without any consequences. If, during any assessment, the project coordinator determines that a participant has developed a serious health problem, efforts will be made to help the participant access appropriate treatment as quickly as possible. In addition, any scans that suggest possible problems are sent to a radiologist for a consult. In the event of a potential problem, [name] will meet with the participant and the radiologist to discuss the findings, per protocol from the Biomedical Research Imaging Center.

## K. Data Collection and Management

All paper data will be stored in a locked filing cabinet in a locked room. All digital data will be stored on servers which require passwords to access. Data will be saved as confidential, coded files. All blood data and genetic data will be de-identified and will be kept in secure freezers until it is assayed.

Only authorized project staff will have access to the information gathered for this project. We will follow established data handling procedures as follows: (a) data will be reported in aggregate form only; (b) all data will be kept in locked file cabinets and/or in password-protected computer files; and (c) all personnel interacting with participants and having access to data are trained in confidentiality procedures.

Any paper documents will be stored in locked files, behind locked doors at the laboratory on campus at UNC-CH. The key that links participant names to the identification numbers will be kept separate from the data, also in a locked file.

fMRI data collected at the BRIC is sent over a secured server (PACS), this data is attached to coded numbers. fMRI data is accessed through this password protected served and transferred to the lab's protected databases. Unprotected personal information of subjects is never sent over the web.

## L. Recruitment Strategy

Recruitment posters will be placed on the UNC campus, in community centers, and restaurants in local Chapel Hill/Durham area. Additionally, we will use the 'UNC-Chapel Hill Biomedical Research Imaging Center (BRIC) Database' (UNC-CH IRB #13-0959) and the 'Join the Conquest' (UNC-CH IRB #13-1768) recruitment databases. These and similar approaches have been successfully used for recruitment in this sampling frame (e.g., R01DK092468, NORC5-34387). Those interested in participating will be directed to the screening website. Information needed to determine participant eligibility will be obtained via web, phone or in person (see attached prescreening material). The subjects will be contacted by research staff via the preferred method of the subject (phone, email, in person) to provide the consent for review and schedule the first assessment (if applicable).

#### M. Consent Process

If the potential participant is interested in the study they will be scheduled for a screening visit and a consent form will be mailed or emailed to them. At the screening visit, before an assessments, the consent form will be reviewed, all answers regarding study expectations will be answered, and consent will be confirmed by trained study staff (listed in the personnel section of the application). Consenting will be performed in a private room.

## **Statistical Analysis Plan**

### **A. Sample Size and Power**

We will recruit and screen 180, 18-35 year old overweight/obese individuals in order to enroll 50 participants with and without the presence of the DRD2 TaqIA A1 allele, and at high risk for T2DM by virtue of HbA1c. The n=42 represents the number of participants who will provide usable data and accounts for possible attrition and negative side effects of the bromocriptine (based on previous repeated measures fMRI studies and reports of bromocriptine, expected attrition is 4%-7%). In evaluating our inclusion/exclusion criteria (see below) conservatively we anticipate 180 participants per year will be eligible for the present investigation. Of those, based on previous work, 36 are expected to have one A1 variant of the TaqIA polymorphism and 144 to have A2/A2 (per each recruitment year). Therefore, over the three-year duration of the present study, we will have ample opportunity to meet our recruitment targets (Y1: n= 17; Y2: n= 18; Y3: n= 15). Power analyses were conducted using fMRIPower (for fMRI contrasts described in Aim 1b) and G\*Power (for lab measures) to determine sample size based on previous work (25). Sample sizes were determined by the between-group (TaqIA allele status; Aim 2) difference, which is the least sensitive of the proposed tests. Based on a small to medium sized effect ( $r = .30$ ), we determined that a similarly sized strategy-by-assignment interaction would be detectable with 0.8 power with at least n=21 per group, yielding a total sample size of 42. To account for the small possibility of complications with blood draws, excessive movement in the scanner, side effects from the medication or other protocol deviations we plan on recruiting a total of 50 (25 per cell).

